## 10.6 Special situations

## Pregnancy

The occurrence of a pregnancy must be reported to Transgene and Transgene's representative by the Investigator using a "Pregnancy form":

- The first part of the form is used to collect information at the beginning of the pregnancy. It should be completed and reported immediately
- The second part of the form is to collect information about the outcome of the pregnancy. It should be reported within the same time frame and even if the patient was withdrawn from the study

Pregnancies have to be followed up to the completion or termination of the pregnancy, collecting information about the pregnancy and knowledge of the newborn medical status. Pregnancy outcomes must be collected for the female partners of any males who took any IMP. Consent to report information regarding these pregnancy outcomes should be obtained from the mother.

Pregnancy itself is not considered as an AE. However, any problem met during the pregnancy should be reported as an AE or a SAE. Spontaneous or induced abortions as well as ectopic pregnancy should be considered as serious.

All pregnancies starting from the first IMP administration and up to 3 months after the last IMP administration must be reported.

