# 1.4.1.1.3 Sequential Therapy

IT Pexa-Vec injections will be performed on D1, D15 and D29. Additional Pexa-Vec boosts may be performed from Week 12 after discussion on a case by case basis between the investigator and Transgene.

Nivolumab will be given from D15, by IV route every 2 weeks until progression or unacceptable toxicity.

The rationale for the sequential administration of Pexa-Vec followed by nivolumab is based on preclinical studies. Rojas et al. (2015) provided the first preclinical data to support the use of oncolytic vaccinia virus in combination with anti-CTLA-4 antibody. In these studies, it was shown that one systemic dose of vaccinia virus followed by three intra-peritoneal doses of anti-CTLA4 therapy could establish significant tumor growth control and increased OS in mice models of renal carcinoma. When the anti-CTLA-4 was administered concurrently with the vaccinia virus, no efficacy was observed.

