## 4.1 Inclusion criteria

Patients must satisfy all of the following criteria for entry into the protocol:

- 1. Male or female patients, age ≥18 years old,
- 2. Histological/cytological diagnosis of primary HCC, excluding cholangiocarcinoma, hepatocholangiocarcinoma, fibrolamellar carcinoma and hepatoblastoma. Note: if no previous pathological report is available, a tumor diagnostic biopsy should be performed,
- 3. Advanced stage HCC per EASL-EORTC (European Association for the Study of the Liver-European Organisation for Research and Treatment of Cancer) guidelines, i.e. patients who are not candidates for curative interventions and not candidates for locoregional modalities,
- 4. Patients naïve to systemic therapy for HCC,
- 5. Tumor status (as determined by radiology evaluation): At least one measurable viable tumor in the liver, ≥1 cm longest diameter (LD), using a dynamic imaging technique (arterial phase of triphasic computerized tomography [CT] scan, or dynamic contrastenhanced magnetic resonance imaging [MRI]), and injectable under imaging-guidance (CT or ultrasound),
- 6. At least one tumor that has not received prior local-regional treatment, or that has exhibited definitive growth of viable tumor since prior local-regional treatment of HCC undertaken at least 4 weeks prior to enrolment or 3 months prior to enrolment for radioembolization,
- 7. Child-Pugh Class A. Note: paracentesis, albumin infusion or diuretic treatment cannot be used to downgrade Child-Pugh score (e.g., to improve from severe to moderate/mild or from moderate to mild ascites),
- 8. Performance status 0 or 1 on the Eastern Cooperative Oncology Group (ECOG) scale,
- 9. Adequate hematological, hepatic, and renal function:
  - a. Hemoglobin ≥9 g/dL
  - b. Platelet count  $\geq 60 \cdot 10^9 / L$
  - c. International normalized ratio (INR) <1.7
  - d. White blood cell (WBC) count  $\geq 2.10^9/L$
  - e. Absolute neutrophil count (ANC)  $\geq 1.10^9/L$
  - f. Albumin ≥28 g/L, total bilirubin ≤1.5 times upper limit of normal (ULN); alanine aminotransferase (ALT), aspartate transaminase (AST) ≤5 ULN

- g. Serum creatinine <20 mg/L or creatinine clearance >60 mL/min according to Cockroft-Gault formula,
- 10. For patients who are sexually active: willing to use adequate barrier contraception method during Pexa-Vec and nivolumab treatment period, for at least 6 weeks after last Pexa-Vec injection and for at least 5 months after last nivolumab administration,

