## 5 INVESTIGATIONAL MEDICINAL PRODUCTS

Pexa-Vec is in development for an advanced HCC patient population in combination with nivolumab. Therefore, in this study Pexa-Vec and nivolumab are considered as Investigational Medicinal Products (IMPs).

Pexa-Vec and nivolumab are provided free of charge by Transgene. The Investigator/Pharmacist will not supply IMP to any patient not included in the study, nor to any physicians or scientists who are not designated as sub-Investigators. The Investigator must ensure that patients receive IMP only from personnel who fully understand the procedures for dosing and administering the drugs.

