## 8.9 Pexa-Vec injection boost Visits

Additional Pexa-Vec boosts may be performed in patients based on a case by case discussion between the investigator and Transgene, on the grounds of individual patient benefit. In any case, Pexa-Vec boosts will be performed no sooner than Week 12 and will be combined with a nivolumab infusion session. At such visits, patients will complete the following procedures:

- Complete physical examination, including weight, vital signs, and ECOG PS
- Skin and mucosal examination; AEs and concomitant medications reporting
- Blood sample collection for the following testing: hematology, chemistry, coagulation and CRP.
- Pregnancy test (urine) for WOCBP (if positive, an ultrasound will be performed to confirm pregnancy).

Patients will be monitored for troponin T or I blood level 3 and 8 days (± 1) after Pexa-Vec administration.

Patients will undergo an ECG 8 days ( $\pm$  1) after Pexa-Vec administration.

Patients will undergo an ECG 3 days (± 1) after Pexa-Vec administration, in case of troponin clinically significant increase.

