## 10.3 Time Period for Collection of AEs and SAEs

From the date of signature of ICF and up to first IMP administration (i.e. before the patient receives any IMP) only SARs caused by a protocol-required procedure (e.g., related to invasive procedures such as blood sampling) will be collected and reported (See sections 9.4 and 9.5). AEs, SAEs, or procedure related ARs that occur during this period, and that are considered by the investigator as relevant to the patient condition, will be collected as a current medical history.

After the initiation of either IMP and up to 28 days after the last dose of IMP, all AEs and SAEs should be collected and recorded on the eCRF. SAEs should also be reported to Transgene.

SAEs occurring more than 28 days after the last dose of IMP, and evaluated by the Investigator as related to the IMP should be collected and reported to Transgene indefinitely even after end of study. Only SAEs occurring prior to end of study will be reported in the eCRF.

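### The only explicit pregnancy-reporting window ends 3 months after the last IMP, 2 months short of the contraception period required after nivolumab

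*Protocol*

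**What the plan says.** Inclusion criterion 10 (protocol synopsis and section 4.1, same durations in both) asks sexually active patients to use contraception during treatment and then "for at least 6 weeks after last Pexa-Vec injection and for at least 5 months after last nivolumab administration".

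Section 10.6, under Pregnancy, opens with a general duty to report a pregnancy, with no date attached. It then asks for follow-up to the end of the pregnancy and adds: "Pregnancy outcomes must be collected for the female partners of any males who took any IMP". It closes with the only sentence that sets a period: "All pregnancies starting from the first IMP administration and up to 3 months after the last IMP administration must be reported".

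Section 5 treats Pexa-Vec and nivolumab alike as IMPs, so the last IMP may be either product. On the schedule, section 1.4.1.1.3 states: "Nivolumab will be given from D15, by IV route every 2 weeks until progression or unacceptable toxicity". Pexa-Vec is planned for D1, D15 and D29. Section 8.9 adds that "Pexa-Vec boosts will be performed no sooner than Week 12 and will be combined with a nivolumab infusion session".

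**The concern.** The two passages set different end dates for what looks like one period of interest. Criterion 10 asks patients, men and women, to avoid conception for 5 months after nivolumab. Section 10.6 expressly requires sites to report pregnancies only if they start within 3 months of the last IMP. A site that uses the closing sentence of 10.6 to decide what must be sent to the sponsor has no express duty to send a pregnancy that began in month 4, in a patient or in a male patient's partner.

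What is at stake is complete safety capture. Safety is the primary objective of the Phase I part and a secondary objective of the Phase IIa part, and section 1.3.1 says that no fertility studies have been done with nivolumab. A conception in those two months would also be a failure of contraception while the protocol still requires it, which the sponsor would want to know about. The ORR design, the DLT rule and the stopping boundaries are not involved.

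**Working it through.** There is no plan figure to reproduce. The check compares two stated durations and then looks for any other rule that would fill the difference.

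**Inputs**
- Contraception after nivolumab: 5 months (criterion 10).
- Contraception after Pexa-Vec: 6 weeks (criterion 10).
- Reporting window: 3 months after the last IMP (section 10.6).
- Month length: 30.4375 days (SAP section 7.7.2).

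**Step 1: which IMP starts the reporting clock.** Nivolumab continues every 2 weeks after the third Pexa-Vec injection on D29, and any boost is tied to a nivolumab session. The last IMP date is therefore normally the last nivolumab date, or within a day of it when the two products are given on consecutive days.

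**Step 2: the gap after nivolumab.**
- 5 × 30.4375 = 152.2 days
- 3 × 30.4375 = 91.3 days
- Difference: 152.2 − 91.3 = 60.9 days, or 5 − 3 = 2 months
- Share of the contraception period: 2/5 = 40%, as calendar time only

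**Step 3: a less usual case.** Assume that nivolumab stopped after D15 and Pexa-Vec was still given on D29. The reporting clock would then start 14 days later, and the gap would be 152.2 − (91.3 + 14) = 46.9 days. It shrinks but stays open.

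**Step 4: Pexa-Vec.** 6 weeks = 42 days, and 42/30.4375 = 1.4 months. That is inside 91.3 days, so there is no gap for Pexa-Vec.

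**Step 5: other routes by which a pregnancy in months 3 to 5 could reach the sponsor.**
- *AE collection (section 10.3).* All AEs are collected up to 28 days after the last dose. After that the rule covers "SAEs occurring more than 28 days after the last dose of IMP, and evaluated by the Investigator as related to the IMP". Section 10.6 does not count a pregnancy in itself as an AE, so an uncomplicated one cannot enter this way. A miscarriage or ectopic pregnancy is classed as serious, but this late it would enter only if judged related.
- *Pregnancy tests (sections 8.1 and 8.12).* Urine tests are done at the 28-day safety visit and at the end-of-study visit. If progression came first, these are one visit, due from 28 days after the last dose. If treatment stopped without progression, the end-of-study visit waits for progression and may fall in months 3 to 5. The tests do not cover partners.
- *Survival contacts (section 8.13).* These take place every 8 weeks and record survival and further anti-cancer therapy only.
- *Long-term follow-up (section 8.14).* A yearly history and examination, in which the trigger for informing the sponsor is an event suspected to be related to Pexa-Vec.

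None of these reliably catches an uncomplicated pregnancy that begins in the gap.

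**The case against.** The strongest reply is that section 10.6 does not stop reporting at 3 months. Its opening duty and its sentence on partners carry no date, and the closing sentence sets a minimum without barring later reports. This stands as far as it goes: a careful site might report a month-4 pregnancy under the opening sentence. A reader might infer that such pregnancies will simply go unreported, and the documents do not support that. They support the narrower statement that no express duty covers them. The reply does not remove the mismatch. If open-ended reporting was intended, the closing sentence obscures it. If 3 months was intended, it is shorter than criterion 10.

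A second reply is that an entry condition on contraception and a reporting duty need not have the same length, and that the protocol never calls the 5 months a risk period. That is correct. This is a misalignment of two obligations, and reading the contraception period as the period of interest is an inference, though a natural one.

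A reader might also point to fetal vaccinia, which section 10.1 lists among the vaccinia complications, as the harm that would be missed. The documents do not support this. It is a Pexa-Vec risk, and the whole post-Pexa-Vec contraception period lies inside the reporting window.

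Finally, there are partial safety nets, namely the end-of-study test, the late related SAEs and the yearly follow-up. They reduce the gap without closing it.

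**Conclusion.** The point holds and is minor. For about 2 of the 5 months after the last nivolumab dose (60.9 days, or 46.9 in the less usual case above), contraception is required but no passage expressly requires a pregnancy to be reported.

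This rests on two assumptions: nivolumab is normally the last IMP, which the schedule supports, and sites will follow the one sentence in section 10.6 that gives a period.

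The 40% is a ratio of calendar time. A reader might take it as a share of events lost, but the documents give no pregnancy rate from which to estimate that. With a maximum enrolment of 47 patients (section 3.1.2), all with advanced disease, few events are expected. No endpoint, sample size or decision rule depends on the gap. Nothing here says whether 5 months or 3 months is the right duration.

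**What to change.** Reconcile criterion 10 (synopsis and section 4.1) with section 10.6, so that the reporting window is at least as long as the contraception window that criterion 10 states. It would help to say in the same sentence that the window covers partners of male patients, since the partner sentence has no period of its own. If the sponsor intended 3 months, the two passages still need to be reconciled.

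Add a pregnancy question to the 8-weekly contacts in section 8.13, because they do not ask about it now. As an illustration, if the safety visit falls on day 28 after the last dose, contacts fall on days 84, 140 and 196 (28 + 56, then steps of 56). The last two could pick up pregnancies that began between days 91 and 152.

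The cost is one amended sentence, one added question and possibly a few more pregnancy forms, with no new visit.

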## **Overdose**

Any overdose should be reported to Transgene and Transgene's representative within 24 hours of occurrence or knowledge of the overdose, and documented and followed-up using an "Overdose form". In addition, any associated symptoms should be reported as an AE or SAE.

# 10.7 Laboratory values, vital signs, physical findings and other safety data

Clinically relevant abnormal laboratory results will be repeated immediately (if relevant) and followed until return to normal unless an adequate explanation is determined, or 28 days after last IMP administration if not related to IMP.

Clinically relevant abnormal findings following vital signs measurements, physical examinations, or ECGs will be reported as AEs or SAEs by the Investigator.

# 10.8 Viral safety and nivolumab safety assessed by blood pharmacokinetics

In Phase I, blood samples for pharmacokinetic analyses will be collected in all patients. Analyses will be performed in all patients within the Recommended Phase II Dose (RP2D) and

RP2D-1 cohorts, and will evaluate the change over time in viral genomes and/or viral infectious units (pfu), and of nivolumab in patient blood samples.

In Phase IIa, blood samples for pharmacokinetic analyses will be collected in all patients. Analyses will be performed in all samples collected. Change over time in viral genomes and/or viral infectious units (pfu), and of nivolumab in patient blood samples will be assessed.

Unscheduled sampling and analyses will be performed only if there is the occurrence of clinical events for which measurement of viral genomes and/or viral infectious units (pfu), and/or nivolumab would be needed for event evaluation.

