#### 6 TREATMENT PLAN

#### 6.1 Treatment administered

### 6.1.1 Treatment regimens

### 6.1.1.1 Phase I part:

Safety and efficacy will be assessed in 6 patients, using a standard regimen for dose level 1 as 3 bi-weekly IT injections of 1x10^9 pfu for Pexa-Vec and 240 mg IV q2weeks for nivolumab (Figure 1: IMP administration scheme).

In case of a Dose-Limiting Toxicity (DLT) is observed in more than one patient out of the first 6 patients, or in the occurrence of a landmark AE, one de-escalation regimen is planned:

• Dose level -1: 3 bi-weekly IT injections of 3x10^8 pfu for Pexa-Vec and 240 mg q2weeks for nivolumab OR 3 bi-weekly IT injections of 10^9 pfu for Pexa-Vec and 240 mg q3 weeks for nivolumab, depending on the DLT profile relative to the known toxicity of each component of the combination, as judged by the Independent Safety Committee (ISC).

A landmark AE is an anticipated effect of the combination, defined as either increase in severity of hepatic cytolysis (doubling of AST – ALT baseline blood concentrations), or significant deterioration of hepatic function (INR, bilirubin), or increase in number or severity of immunerelated AEs, or increase in number or severity of Pexa-Vec-related skin lesions.

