# 6.2 Recommended Phase II dose (RP2D)

In the Phase I part, all patients will be monitored up to D29 for the occurrence of DLTs that defines the DLT period. The RP2D is defined as the maximum dose level (1 or -1) at which a DLT attributable to the IMPs is observed at most in one patient out of 6 patients in the DLT period and upon final recommendation of the ISC that will prevail.

The **DLTs**, applicable for the Phase I part of the study, are defined as such:

- 1. All Grade 3-4 non-hematologic toxicity that represents a 2-grade increase over baseline, excluding:
  - Untreated or inadequately treated nausea, vomiting and diarrhea,
  - Untreated or inadequately treated fever > 40.0°C lasting less than 24 hours (Grade 3); only fever > 40.0°C lasting more than 24 hours (Grade 4) qualifies for DLT,
  - Alopecia,
  - Grade 3 fatigue that returns to grade 2 or less within 7 days,
  - Grade 3 laboratory/metabolic abnormalities, other than ALT or AST, that are not considered clinically significant and that return to grade 2 or less within 72 hours.
- 2. Any Grade ≥ 3 treatment-related acute immune-related AE involving major organs, such as: immune-related pneumonitis, colitis, nephritis, hepatitis, endocrinopathies, immune-related rash and other rare but severe immune-related reactions.
- 3. Grade  $\geq$  3 injection site reaction.
- 4. AST or ALT  $\geq$  10xULN, even if asymptomatic, unless it is related to a definite progression of liver metastases or another clearly identifiable etiology; doubling of AST or ALT that is concurrent with a doubling of the total bilirubin.
- 5. Any toxicity at least possibly related to study therapy that results in a delay in treatment of 2 or more weeks.
- 6. Hematological:
  - Grade ≥ 3 or ≥ 2-grade increase over baseline of neutropenia lasting for more than 7 days.
  - Neutropenic fever.
  - Grade 4 thrombocytopenia or grade 3 thrombocytopenia with clinically significant bleeding.
- 7. Cardiac: association of the 3 following cardiac abnormalities
  - Left ventricular ejection fraction (LVEF) less than the lower limit of normal (LLN), as
    assessed by echocardiography and symptomatic due to drop in ejection fraction,
    responsive to intervention,
  - Increase of blood troponin T or I above the upper limit of normal (ULN),
  - Any ECG abnormality consistent with a Grade 3 cardiac disorder.

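### Protocol 10.8 schedules Phase I PK analysis only for the RP2D and RP2D-1 cohorts, which leaves out dose level 1 if that level fails on DLTs

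*Protocol*

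**What the plan says.** Protocol 10.8 deals with viral and nivolumab safety through blood PK. On sampling it says: "In Phase I, blood samples for pharmacokinetic analyses will be collected in all patients". On analysis, one sentence restricts the set. It opens with "Analyses will be performed in all patients within the Recommended Phase II Dose (RP2D) and", and its second half then names a further group: "RP2D-1 cohorts, and will evaluate the change over time in viral genomes and/or viral infectious units (pfu), and of nivolumab". For Phase IIa there is no such restriction: "Analyses will be performed in all samples collected". The section closes with an event-driven provision: "Unscheduled sampling and analyses will be performed only if there is the occurrence of clinical events" for which a viral or nivolumab measurement is needed.

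Three other sections fix what the cohort labels mean.

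- Protocol 6.2: "The RP2D is defined as the maximum dose level (1 or -1) at which a DLT attributable to the IMPs is observed" in no more than one of 6 patients. The final recommendation of the Independent Safety Committee (ISC) prevails.
- Protocol 6.1.1.1: the starting regimen is level 1. If more than one of the first 6 patients has a DLT, "or in the occurrence of a landmark AE, one de-escalation regimen is planned", namely level -1.
- Protocol 6.3.1: the Phase I cohorts are dose levels 1 and -1. No other level is listed.

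Protocol 9.3 says that PK of both products will be assessed in the trial, with no cohort restriction. The SAP text available to us contains no PK analysis. The text under Protocol 11.1 and 11.2 is not available, and nothing below rests on its absence.

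**The concern.** Analysing the recommended dose and the level below it covers the relevant patients when dosing climbs towards the recommended dose. Here dosing can only go down. If level 1 proves too toxic, level -1 becomes the recommended dose and the only other Phase I cohort lies above it, outside the stated set. In the DLT-driven case the restriction therefore removes the cohort whose toxicity caused the reduction, from an analysis whose stated purpose is safety.

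Two things would be lost from the planned analysis: exposure to virus and nivolumab across the level 1 cohort, including patients without events who serve as the comparison, and any Phase I comparison of exposure between the two dose levels.

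**Working it through.** **Inputs.** One starting level and one reduced level (Protocol 6.1.1.1 and 6.3.1); 6 evaluable patients per cohort (Protocol 6.6.2); RP2D as defined in Protocol 6.2; PK analysis set as in Protocol 10.8.

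**The plan's own counts.** Protocol 3.1.2 gives 6 to 12 evaluable Phase I patients: 6 × 1 = 6 and 6 × 2 = 12. Adding 30 for Phase IIa gives 30 + 12 = 42, and 42 / (1 − 0.10) = 46.7, rounded up to 47. All agree with the protocol.

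**Applying the RP2D definition to each Phase I outcome.** A level passes if at most one of 6 patients has a DLT. The analysis set is the RP2D cohort plus the cohort one level below it, if that cohort was opened.

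| Phase I outcome | Enrolled | RP2D | Level below RP2D | Scheduled for PK analysis |
|---|---|---|---|---|
| Level 1 passes, no reduction | 6 | 1 | -1, not opened | 6 of 6 |
| Level 1 fails on DLTs, level -1 passes | 12 | -1 | none exists | 6 of 12 (level 1 left out) |
| Both levels fail on DLTs | 12 | none | none | 0 of 12 |
| Reduction on a landmark AE alone, RP2D stays at 1 under Protocol 6.2 | 12 | 1 | -1 | 12 of 12 |
| Reduction on a landmark AE alone, ISC names -1 | 12 | -1 | none exists | 6 of 12 (level 1 left out) |

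The fourth row follows because Protocol 6.2 defines the RP2D by DLTs only, whereas the reduction rule in Protocol 6.1.1.1 also responds to landmark AEs.

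**How often level 1 would fail on DLTs.** The documents give no expected DLT rate, so the true rate p is an assumption. With 6 patients, P(2 or more with a DLT) = 1 − (1 − p)^6 − 6p(1 − p)^5.

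- p = 10%: 1 − 0.5314 − 0.3543 = 11.4%
- p = 20%: 1 − 0.2621 − 0.3932 = 34.5%
- p = 30%: 1 − 0.1176 − 0.3025 = 58.0%
- p = 40%: 1 − 0.0467 − 0.1866 = 76.7%

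**After the change.** If all treated Phase I patients are analysed, coverage is 6 of 6 or 12 of 12 in every row.

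**The case against.** The strongest reply is that Protocol 10.8 already allows unscheduled analyses when a clinical event calls for them, and a patient with a DLT is the obvious candidate. This stands in part. A reader might infer that every patient whose toxicity triggered the reduction would go unanalysed; the documents do not support that. But the clause works event by event and depends on a judgement of need. It does not assure analysis of the level 1 cohort.

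A second reply is that the two labels may have been meant simply as names for level 1 and level -1, which would cover everyone. Protocol 10.8 speaks of cohorts, and Protocol 6.3.1 lists exactly those two. The reading is possible but conflicts with Protocol 6.2, under which the RP2D can itself be level -1. What can be shown is wording that needs reconciling, not a decision to discard samples. That the sentence was carried over from an escalation trial is also only an inference, although Protocol 3.2 says that the design derives from a 3+3 escalation and Protocol 10.9 still refers to an escalation cohort.

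A third reply is that the PK detail may sit in Protocol 11.1 and 11.2, which cannot be checked here. That is a real limit, but the restriction in Protocol 10.8 is explicit and would still have to be reconciled with any fuller text.

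Finally, a reader might infer that the rule withholds PK results from the ISC when it chooses which component to reduce. The documents do not support this. They base that choice on the DLT profile against the known toxicity of each component, no visible text makes PK an input, and the RP2D is settled only after the ISC has advised. Supplying PK to the ISC would be a separate proposal and is not made here.

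**Conclusion.** The point holds, with conditions. As written, a DLT failure at level 1 followed by a pass at level -1 leaves 6 of 12 Phase I patients without scheduled cohort-wide PK analysis, and a failure at both levels leaves all 12 without it. These counts assume 6 patients per cohort, the literal definition in Protocol 6.2, and no ISC recommendation that departs from it.

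It would be too strong to say that any de-escalation loses half of the Phase I patients. After a landmark AE alone, level 1 still meets the RP2D definition if at most one patient had a DLT, and all 12 are then covered unless the ISC names level -1.

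The gap concerns planned analysis, not sampling, so it can be closed as long as the samples are kept. It touches neither the primary endpoints nor the DLT rule. It merits correction because the restriction bites in the toxic scenario that a safety PK analysis should cover, and because Phase IIa carries no matching restriction.

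**What to change.** Reconcile Protocol 10.8 with Protocol 6.2 and 6.3.1 by replacing the cohort restriction with a statement that PK analyses of virus and nivolumab will be performed in all treated Phase I patients at every dose level. This no longer depends on which level becomes the RP2D and brings Phase I into line with Phase IIa. Any PK text in Protocol 11.1 and 11.2 should be checked for the same restriction.

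The cost is one amended sentence and, if a reduction occurs, assays on samples already collected from about 6 more patients (up to 12 if both levels fail). Sample size, alpha, power, dosing and patient burden do not change.
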